| Heart Disease Spinal Stenosis A fibrillation Post-op bowel surgery | surgery Hypercholesterolemia Dehydration Hypo/Hyperthyroid Congestive Heart Failure | Peripheral Arterial Syncope Renal Failure-no dialysis |

The diagnoses most commonly reported for home health patients are diabetes, hypertension, heart failure, chronic ulcerative wounds, and osteoarthritis.

5. Be ambulatory without human assistance prior to hospitalization and be able to maintain a gait speed between 0.3 m/s-1.0 m/s at baseline assessment. Gait speed test may be administered in hospital to determine study eligibility.

Inclusion Criteria for Caregivers:

• Primary caregiver for an enrolled participant in the study

Exclusion Criteria for Veterans/spouse of Veteran (one or more):

- 1. Acute lower extremity fracture with weight-bearing restriction
- 2. Elective joint replacement surgery

- 3. Lower extremity amputation
- 4. Acute cardiac surgery
- 5. Terminal illness or end stage kidney disease requiring dialysis
- 6. Alzheimer's Disease
- 7. Deep vein thrombosis/pulmonary embolus VT/PE
- 8. Recent stroke
- 9. Progressive neurodegenerative diagnosis (e.g. Parkinson's, MS, ALS)
- 10. Active involvement of Adult Protective Services
- 11. Active cancer treatment in which exercise is contraindicated
- 12. Currently enrolled in home health physical therapy upon admission to VAMC

13. Clinical discretion of study physician to exclude patients who are determined to be unsafe and/or inappropriate to participate in high intensity rehabilitation as defined by the inclusion/exclusion criteria

Additional exclusion assessed prior to randomization: the inability to ambulate ten feet with human assistance.

Exclusion Criteria for Caregivers:

• Being on probation or alternative prison sentencing.

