D2.5. Intervention: Patients in the PHIT exercise group will receive between 10 and 12 PT visits in their home (45-60 min/session). Data from 3 local home health agencies indicated that the average number of physical therapy visits per episode of care was 8.5 (Agency 1), 7.8 (Agency 2), and 8.6 (Agency 3). Furthermore, the average number of PT visits from the preliminary data for the PHIT and UC groups were 9.8 and 8.4 visits, respectively. Therefore, we chose to target 10-12 PT visits for the proposed study to operate within a reasonable range of the current standards of care and maximize the benefits of the PHIT intervention. Our preliminary data suggest that this frequency of visits (10-12 visits over 4 weeks) will produce neuromuscular and physiological changes that will translate to improved function. Patients in the PHIT group will receive 3-4 visits per week for the first two weeks and 2 visits per week, on non-consecutive days for the remaining 2 weeks (total=10-12 visits). The intervention will consist of progressive resistance exercises for the lower extremity with a portable training device (Shuttle Mini-Press), a motor control-based program of gait/balance training, and ADL training—all designed to

improve mobility (see Table 2; Appendix). PHIT participants will also receive specific written nutritional education to emphasize the importance of increasing protein intake by 15 grams/day to support participation in the high intensity program (see Appendix).

The patients in the UC group will also receive 10-12 visits to match the PHIT group over 4 weeks. We will provide a standardized rehabilitation protocol for the UC group to perform over the 10-visit intervention period, which consists of a controlled low intensity program with activities from each of the domains included in the PHIT program (see Appendix). Both groups will also receive a standardized simple home exercise program, which will include identical exercise activities that differ only on intensity (See Appendix).

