The motor control system of PHIT mobility training begins with exercise tasks requiring low skill and progresses to more skilled movements as previously described.^{68,69} For example, the patient is instructed to step to a visual target placed in different positions. Stepping activities are performed repeatedly in one direction or to one side, then to the opposite side. As performance becomes skilled (i.e., accurate and smooth), then alternating stepping activities are attempted. Walking activities are also progressed from low skill (e.g., walking in a straight line) to more skilled activities such as walking in a serpentine pattern. Progression is based on increasing speed, accuracy, and finally with holding or manipulating of an object (dual task). Each session begins with practicing a "well-learned task." Patients are progressed when performance of the task is 80-100% correct. As walking ability improves, this training begins to target patient endurance by prescribing daily walking programs for two 10 minute bouts and increasing to 20 minutes continuous. Before discharge from home therapy, patients will begin to transition to an unsupervised physical activity program by performing a daily walking program and independent home exercises.

The **PHIT Activity of Daily Living (ADL) training** focuses on increasing mobility in activities needed in daily life. Training in ADLs emphasizes safety and compensation strategies to

maximize independence. Activities include bathroom transfers, bed mobility (e.g. rolling, supine \rightarrow sit), and car transfers. These activities will be delivered at higher intensities than UC as described above in section D.1.2.

Nutritional Education Specific to PHIT Program: While all Veteran participants will receive nutrition screening and education at baseline, those randomized to the PHIT group will have ongoing nutritional education from the interdisciplinary team and be encouraged to supplement protein intake by at least 15g/daily to support participation in higher intensity exercise strategies.^{76,77} Written education about what foods contain at least 15g of protein will be provided to all PHIT group participants. Along with the rest of the interdisciplinary team, physical therapists will follow up on this education and document compliance each visit (see Appendix).

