We have established the following apriori stopping criteria for removing a Veteran from the study to maintain the safety of the participant.

Participants will be withdrawn from the study by the investigators if:

a.) They are admitted to the hospital after enrollment and the study physician determines the Veteran unsafe or inappropriate for high intensity rehabilitation as defined by the inclusion/exclusion criteria

b.) They develop a new medical or psychiatric condition after enrollment which precludes participation in exercise training based on ACSM criteria or the determination of a physician, safety officer, or investigator (i.e. new cardiac diagnosis such as unstable angina, marked change in cognition, acute illness, pneumonia)

Expected Adverse and Serious Adverse Events:

The following are expected AEs and SAEs for this study: High risk behavior, e.g. drug use and/or alcohol abuse; hospitalizations due to poor functional mobility, e.g. falls; and complication from or exacerbation of current medical diagnoses and comorbidities.

Data Management Risks: As with any study, there is a risk of data breach or disclosure of study data outside the study team (e.g through accidental loss of data, theft, inadvertent electronic or paper disclosures). We will minimize these risks through the following protocol for collecting data:

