Missing Data. All patients with outcome measurements will be included in the intent-to-treat analysis. Although we will encourage patients to be fully compliant to their assigned treatment regimen and testing sessions, they will not be dropped from follow-up measurements for lack of compliance. Although statistical methods can be used to "adjust" for missing data, these methods rely on the untestable assumption that data are "missing at random" so that the effect of the missingness can be removed through statistical modeling. We will instead focus on preventing missed follow-up visits and evaluate missingness to determine whether the data are consistent with the hypothesis of missing at random or missing completely at random.

F. Data Analysis Plan:

Primary and Secondary Outcomes: The primary outcome for this study is gait speed measured 60 days following hospital discharge. Secondary outcome measures include SPPB measured at other study time points, mPPT, LSA, NEADL, VR-12, and CBI, measured at designated study time points (see Table 3). The 60 day time point is chosen for clinical relevance because it helps establish not only efficacy but also sustainability of the effects after the initial 30-day intervention period. Preliminary descriptive and graphical analyses (including boxplots, scatterplots, profile plots) will be used for data cleaning and visualization.

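### The stopping criteria remove participants from the study, not only from exercise, so people with a health event before day 60 drop out of the primary intent-to-treat test

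*Combined protocol and SAP*

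**What the plan says.** The stopping criteria (section IV.C) begin "Participants will be withdrawn from the study by the investigators if" and give two triggers:

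- (a) a hospital admission after enrollment, where in addition "the study physician determines the Veteran unsafe or inappropriate for high intensity rehabilitation as defined by the inclusion/exclusion criteria". This is the standard of exclusion item 13 in section IV.B ("determined to be unsafe and/or inappropriate to participate in high intensity rehabilitation as defined by the inclusion/exclusion criteria"), and it is the same for both arms.
- (b) "They develop a new medical or psychiatric condition after enrollment which precludes participation in exercise training".

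Both triggers are dated only as after enrollment.

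Supervised exercise lasts about four weeks in both arms. D2.5 says of usual care (UC) "The patients in the UC group will also receive 10-12 visits to match the PHIT group over 4 weeks", and the Data Analysis Plan (section F) justifies the 60-day endpoint by the "sustainability of the effects after the initial 30-day intervention period". As the supervised visits draw to a close, "patients will begin to transition to an unsupervised physical activity program by performing a daily walking program and independent home exercises". Follow-up visits are at 30, 60, 90 and 180 days (D2.1).

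Section D, Missing Data, states "All patients with outcome measurements will be included in the intent-to-treat analysis". It promises continued follow-up only to participants who do not comply, and it prefers preventing missed visits and examining missingness to statistical adjustment. The primary analysis in section F is a single regression test of 60-day change in gait speed. The repeated-measures model is secondary.

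Adverse events are collected by a script given seven times (section IV.A) and compared between arms by a likelihood ratio test (section F). The sample size text in section F uses re-hospitalization as its example of a Veteran being lost to the study.

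**The concern.** The rule treats being unfit for exercise as a reason to leave the trial altogether. An intent-to-treat comparison needs outcomes from everyone randomised, including people who stop treatment for health reasons. Here the loss is selected by a health event after randomisation, and hospitalization or acute illness is plausibly related to walking speed.

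The primary mean difference stays unbiased only if the withdrawal rate, the prognosis of those withdrawn, and the treatment effect in them match across arms and with those retained. If PHIT loses more poor performers, its benefit is overstated. If UC does, it is understated.

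Safety is the second stake. Aim 1 asks whether PHIT is as safe as UC, and Hypothesis 1.1 predicts no increase in adverse events. Follow-up is least assured in the people who have just had an event, so repeat events may be missed.

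The rule also works against the Missing Data section: the plan relies on preventing missed visits, yet has the investigators end them.

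**Working it through.** **1. Who is absent from the primary test.** The response variable is 60-day change in gait speed. A participant who completes every supervised visit, is admitted on day 45 and is judged unfit would be withdrawn before the day-60 visit and have no response value. The retention promise does not help, because it covers non-compliance only.

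**2. Timing.** Inputs: supervised exercise about 30 days, primary endpoint day 60, follow-up to day 180.

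- Share of the pre-endpoint period after supervised exercise: (60 − 30)/60 = 50%.
- Share of all follow-up after supervised exercise: (180 − 30)/180 = 83%, or 150 days. Of these, 180 − 60 = 120 days fall after the primary endpoint. Withdrawal then cannot affect the primary test, but it does affect later outcomes and safety.

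**3. Follow-up not provided for, per person withdrawn.** Table 1 gives four post-baseline outcome visits (30, 60, 90, 180). The adverse-event script is given at baseline and days 30, 60, 90, 120, 150 and 180.

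| Withdrawn | Outcome visits lost | Adverse-event contacts lost |
|---|---|---|
| Before day 30 | 4 of 4 | 6 of 7 |
| Days 30-60 | 3 of 4, including the primary visit | 5 of 7 |
| Days 60-90 | 2 of 4 | 4 of 7 |

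**4. Power.** Inputs from the sample size text: difference 0.18 m/s, SD 0.29 m/s, two-sided alpha 0.05, two-group t-test, 112 completers.

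- Plan's figure: noncentrality = 0.18/(0.29 × √(2/56)) = 3.28, giving 90.2% power. The stated 90% is reproduced.
- Enrollment: 112/(1 − 0.25) = 149.3, rounded up to 150. The allowance is 150 − 112 = 38 people.
- Stress case: D2.3 cites re-hospitalization of 20-30% among home care recipients. Applying 30% to the 150 enrolled and withdrawing all of them is an assumption. It gives 0.30 × 150 = 45 lost and 105 left, noncentrality 0.18/(0.29 × √(2/52.5)) = 3.18, and power 88.3%, before other losses.

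**5. Bias (all inputs assumed).** Let w be the share withdrawn before day 60 in an arm, and g the mean 60-day change in those retained minus that in those withdrawn. Then

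bias = (retained-only difference) − (all-randomised difference) = w_PHIT × g_PHIT − w_UC × g_UC.

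| w PHIT / UC | g PHIT / UC (m/s) | Bias (m/s) |
|---|---|---|
| 10% / 10% | 0.20 / 0.20 | 0 |
| 15% / 5% | 0.10 / 0.10 | +0.01 |
| 15% / 5% | 0.20 / 0.20 | +0.02 |
| 15% / 5% | 0.30 / 0.30 | +0.03 |
| 15% / 5% | 0.30 / 0.10 | 0.045 − 0.005 = +0.04 |
| 5% / 15% | 0.10 / 0.30 | −0.04 |

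Equal rates do not guarantee zero bias. With 10% withdrawn in each arm, the same underlying prognosis, an effect of 0.18 in those retained and none in those withdrawn, g differs by 0.18 between arms and the bias is 0.10 × 0.18 = +0.018 m/s.

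**6. Safety data.** The script is the only source that the plan names for systematic adverse-event collection, and it is not said to continue after withdrawal. Section IV.C allows extraction of medical data from the VA EMR, but does not name it as an adverse-event source or say that it continues for those withdrawn. If the adverse-event rates use time at risk, which is not stated, follow-up before withdrawal still counts.

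**The case against.** The wording of the rule is not in dispute. The objections concern how much it matters.

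- **Withdrawal is not automatic.** Trigger (a) also needs a physician's determination, and (b) a condition that rules out exercise. This stands: the number affected is unknown.
- **Exercise does not clearly end at day 30.** Both arms have a home program, and the script asks about exercise at each contact. This stands, and it weakens the timing argument. A reason to stop exercise is still not a reason to stop measuring.
- **The analysis partly copes.** The repeated-measures model can use day-30 data from people withdrawn later, and missingness will be examined. But the conclusion rests on the single primary test. It is true that everyone enrolled has a baseline measurement, so the intent-to-treat sentence can be read as covering them. The exclusion then comes from the 60-day response variable, with the same result.
- **Differential withdrawal is speculative.** One standard serves both arms, D2.6 limits knowledge of assignment, and patients are asked not to share it in care coordination meetings. This makes bias a risk, not a certainty.
- **The triggering admission is known to investigators,** therapists monitor participants, and physicians remain involved. The gap therefore concerns events after withdrawal.
- **Little may be recovered.** The background section places all testing at home, so people who cannot be tested, or who are in a facility at day 60, will still lack gait speed. This stands.
- **The Appendix and consent pages are not visible** and could provide for later follow-up.

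**Conclusion.** The concern holds and should be fixed. As written, the plan removes people selected by a health event after randomisation from a test it calls intent-to-treat, and makes no visible provision for following them. That conclusion rests on the text alone.

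The size is uncertain. Under the assumed inputs the bias runs from 0 to ±0.04 m/s, below the 0.1 m/s important difference, and its direction is unknown. Those figures are illustrative and assume 5-15% withdrawn per arm with a gap of 0.10-0.30 m/s. Loss of power is secondary, because dropout of 25% is already budgeted. For safety, a participant withdrawn before day 60 has five or six of seven adverse-event contacts not provided for.

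**What to change.** Reconcile the stopping criteria with the Missing Data section and the Data Analysis Plan:

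1. Separate discontinuing study exercise from withdrawing from follow-up.
2. State that, in both arms, participants who meet (a) or (b) remain in the already-scheduled outcome visits and adverse-event contacts to day 180 unless consent is withdrawn, and stay in the intent-to-treat analysis.
3. State whether EMR extraction is an adverse-event source, and whether it continues for these participants.
4. Align the re-hospitalization example in the caregiver text with this.
5. Report the number and timing of exercise discontinuations and of study withdrawals by arm.

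The clinical criteria for stopping exercise, who decides them, and which tests a participant can safely perform remain with the sponsor.

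The cost is protocol wording plus some already-planned visits and calls in sicker participants, which adds to their burden. No new procedure is needed. Some day-60 gait speeds will still be missing.

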The **St. Louis University Mental Status Examination (SLUMS)** screens for cognitive impairment by assessing participant function in the areas of attention, calculation, immediate and delayed recall, animal naming, abstract thinking and visuospatial skills.⁶⁴ Patient examination with the SLUMS test is used in both clinical and research settings to screen for dementia. The SLUMS test has strong concurrent validity with the Mini-Mental Status Examination, and is a reliable screening tool for the presence of cognitive impairments with a reported sensitivity of 95-98% and a specificity of 76-100%.⁶⁵

The **Patient Activation Measure (PAM)** identifies patient motivation levels regarding their healthcare. The PAM tool can reliably predict future ER visits, hospital admissions, and medication/ therapy adherence. The survey classifies patient activation levels on a scale from 1 (low activation/motivation) to 4 (high activation/motivation). Patients who score higher on the PAM survey tend to be hospitalized less and adhere to medication and therapy schedules more.

B. Description of Population to be Enrolled:

In this study, the target population is community-dwelling older Veterans or spouses of Veterans, 55 years of age and older, who either were hospitalized or who are medically deconditioned (experienced a decline in physical function) as a result of physical activity restrictions due to COVID-19), have several comorbid conditions, and are eligible for home health physical therapy. These patients will either provided with a COMIRB approved flyer describing the study or will be approached in the hospital and asked if they would agree to participate in a study examining the effects of Usual Care (UC) vs progressive high intensity therapy (PHIT) intervention following hospitalization.

Formal inclusion/exclusion criteria are:

Inclusion Criteria for Veterans/spouse of Veteran (All criteria must be met):

- 1. Veteran status or spouse of Veteran
- 2. 55 years of age and older
- 3. Eligible for home care physical therapy
- 4. Have at least 3 comorbid conditions including those listed below:

| o COPD | Gastrointestinal Bleed | Urinary Tract Infection |
|---|---|---|
| Pneumonia Hypertension Hernia | Chronic ulcerative Depression/mental Post-op pancreatic | Diabetes Irritable Bowel Syndrome Osteoporosis/OA/RA/Gout |

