Finally, training in activities of daily living (ADLs) remains a fundamental element of all home therapy and represents the third, important component of the PHIT intervention. Training in activities of daily living emphasizes safety and compensation strategies to maximize independence as well as reinforce the gains made through progressive resistance exercise and motor control components of intervention. In general, our ADL training will be carried out as a task specific training program consisting of coordinated, multi-joint movement patterns that simulate the functional patterns required for independence in the home setting⁷² (i.e., transfers in and out of bed and sit to stands from seating surfaces within the Veteran's home environment). The PHIT program will perform this task-specific ADL training at high intensity; each task performed will be dosed at the equivalent of an 8-10 RM resistance exercise. Task specific training in homebound Veterans at this intensity is likely to facilitate greater improvements in strength, power, and coordination in important functional patterns, and thus carry over to improved ADL performance.

D2.1. Design Overview

We propose to conduct a single blind, randomized controlled trial in 150 older Veterans with multiple chronic conditions discharged from acute care or medically deconditioned, and referred to home health physical therapy. The two arms will include a PHIT progressive multi-component physical therapy program and a documented UC physical therapy intervention. Veterans

admitted to the Denver VAMC will be evaluated for eligibility. Following consent, eligible patients be randomized to either treatment group by the home health coordinator who holds the randomization list. Following hospital discharge, a baseline assessment will be performed within 48 hours of returning to their home. Follow-up assessments will occur at 30, 60, 90, and 180 days following hospitalization (see Figure 1; specific aims). Medically deconditioned participants will complete the same study visit schedule of a baseline assessment with follow-up visits at 30, 60, 90, and 180 days following baseline.

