Primary Analysis (Aim 1): The primary analysis will be an intent-to-treat comparison of the differences between treatment groups in change in gait speed 60 days following hospital discharge. Statistical inference regarding the difference between treatment groups will be based on the estimated coefficient for a treatment group indicator variable in a linear regression model with 60 day change in walking speed as the response variable, and explanatory variables that include an indicator of treatment group and the baseline value of gait speed. The baseline gait speed value is included to improve the precision/power of the inference about treatment differences. The conclusion about the statistical significance of differences between groups will be determined by this single statistical test to protect against an elevated risk of false-positive conclusions. Sensitivity analysis will be done to evaluate whether conclusions would differ when other important covariates are added to the model (length of hospital stay, inflammatory molecules, presence of the frailty phenotype [Fried's criteria⁸⁴], days of intensive care unit stay, days of inpatient rehabilitation, age, comorbidity burden, social status, gender]. These variables will be extracted from the VA EMR and stored in the VA version of RedCAP using unique ID numbers for each Veteran. Secondary Analyses (Aim 2): Differences between groups at 60 days following hospital discharge in other outcomes (SPPB, mPPT, PA, dynamometry, LSA, PAM NEADL, CBI, SLUMS, and VR-12) will be analyzed as described above. Follow-up measures at 90 and 180 days will be analyzed to evaluate the long-term impact and sustainability of our PHIT interventions. Secondary analyses will be evaluated for their consistency with the conclusions of the primary endpoints. We anticipate that group differences in secondary measures will be correlated with the primary so that significant differences in the primary endpoint will be reinforced by similar effects on secondary endpoints. Failure to observe consistency in the primary and secondary endpoints will be taken as evidence that the effects of PHIT are not clear, and that further study is necessary to resolve any inconsistencies. This approach will reduce the risk of false-positive conclusions resulting from multiple statistical tests.

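### Entry was widened to people never hospitalised, but the endpoint wording, Aim 1 and the planned models still assume a hospital discharge and leave out entry route

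*Combined protocol and SAP*

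**What the plan says.** **Who is enrolled.** Section B (Description of Population to be Enrolled) takes people "who either were hospitalized or who are medically deconditioned (experienced a decline in physical function" because of COVID-19 activity restrictions. D2.1 (Design Overview) and D2.2 (Eligibility Criteria) also cover this second route.

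**When they are seen.** D2.1 sets out two clocks. For discharged participants, "Follow-up assessments will occur at 30, 60, 90, and 180 days following hospitalization", and "a baseline assessment will be performed within 48 hours of returning to their home". The others have a baseline and "follow-up visits at 30, 60, 90, and 180 days following baseline".

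**What is analysed.** Section F (Data Analysis Plan) states: "The primary outcome for this study is gait speed measured 60 days following hospital discharge". The primary analysis regresses 60-day change in gait speed on "explanatory variables that include an indicator of treatment group and the baseline value of gait speed". The listed sensitivity covariates include length of stay, ICU days and inpatient rehabilitation days, but no indicator of entry route. Aim 1 in section I concerns therapy begun on leaving an acute care hospital.

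**How they are randomised.** D2.3 describes random blocks of 4 and 6 and states no stratification by entry route.

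**The concern.** The population changed and the analysis section did not follow. Three consequences are visible.

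- **Who counts in the primary analysis.** The endpoint as worded in section F starts at an event that some participants never had. The Missing Data paragraph includes every patient with outcome measurements, while Aim 1 addresses only those discharged. One analyst could keep everyone and another could keep only discharged participants, each citing the plan. The primary conclusion rests on a single test, so this should be settled before unblinding.
- **A baseline factor is unused.** Route is known for everyone at entry and may be related to 60-day change. The plan includes baseline gait speed to gain precision, and the same reasoning covers route.
- **The pooled estimate has no companion.** If the effect of PHIT differs by route, the pooled estimate averages over whatever mix was enrolled. No planned analysis isolates the population that Aim 1 names.

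**Working it through.** **Inputs from the documents (Sample Size Estimates):** difference 0.18 m/s, SD 0.29 m/s, 56 completers per group, two-sided alpha 0.05, two-group t-test, stated power 90%.

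**Inputs that are assumed:** *p*, the share of non-hospitalised participants, 10–50%; *D*, the difference between routes in mean 60-day change, 0.1–0.2 m/s. The documents give neither.

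**Step 1: the plan's own figure.** SE = 0.29 × √(2/56) = 0.0548. The noncentral t with 110 df gives power 90.2% (normal approximation 90.7%). The stated 90% is reproduced.

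**Step 2: power lost if 0.29 is the SD within a route.** This is plausible because the pilot studied post-hospital patients. Without a route term the SD becomes √(0.29² + p(1−p)D²). With the term it stays at 0.29 and power stays at about 90.2%.

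| p | D (m/s) | SD without route | Power without route (t-test) |
|---|---|---|---|
| 0.1 | 0.1 | 0.2915 | 89.9% |
| 0.2 | 0.1 | 0.2927 | 89.7% |
| 0.3 | 0.2 | 0.3041 | 87.4% |
| 0.5 | 0.2 | 0.3068 | 86.8% |

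The loss is 90.2 − 89.9 = 0.3 points at the mild end and 90.2 − 86.8 = 3.4 points at the extreme.

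**Step 3: power gained if 0.29 is instead the total SD.** Route then explains R² = p(1−p)D²/0.29², and the adjusted SD is 0.29 × √(1−R²).

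- p = 0.1, D = 0.1: R² = 0.09 × 0.01/0.0841 = 1.1%; power rises from 90.2% to 90.5%.
- p = 0.5, D = 0.2: R² = 0.25 × 0.04/0.0841 = 11.9%; power rises from 90.2% to 93.4%.

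**Step 4: validity.** A simulation of 8,000 trials used N = 112, unstratified blocks of 4 and 6, p = 0.3 and D = 0.20.

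| | Route omitted | Route included |
|---|---|---|
| Mean estimate (true effect 0.18) | 0.180 | 0.180 |
| Type I error | 5.2% | 5.2% |
| Power | 87.0% | 89.9% |

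Omission leaves the comparison unbiased and the test level intact.

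**Step 5: the two clocks.** Discharged participants have baseline within 48 hours of returning home. When the schedule is kept, day 60 from discharge and day 60 from baseline therefore differ by about 2 days at most.

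**Step 6: what a discharged-only analysis can show.** The number per group is 56 × (1−p). The approximate 95% half-width is 1.96 × 0.29 × √(2/n), which is 0.107 m/s for all 56 per group. At p = 0.1 (about 50 per group) it is 0.113; at p = 0.5 (28 per group) it is 0.152.

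**The case against.** The best defence is that nothing is broken. D2.1 supplies a clock for the second group, the response variable in section F is a 60-day change that can be computed for both groups, and randomisation protects the comparison. Adjusting for one more baseline factor is good practice, but omitting it is not an error. All of this stands, and it limits the point. Several stronger readings are tempting but not supported:

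- **That non-hospitalised participants have no primary endpoint.** A reader might infer this from section F alone. D2.1 gives them a day-60 visit from baseline, so the fault is wording that lags behind the design.
- **That recovery differs by route.** No section reports change by route, and the pilot results are not split this way. The protocol describes usual-care performance worsening from 30 to 60 days in the pilot, which gives little support to assuming spontaneous recovery after discharge. A value of D = 0.2 m/s would exceed the planned treatment effect of 0.18 m/s.
- **That chance imbalance in route distorts the estimate.** At p = 0.5 and D = 0.2, a 95%-range imbalance is 1.96 × √(0.25 × 2/56) = 18.5 percentage points, which moves an unadjusted estimate by 0.185 × 0.2 = 0.037 m/s, or 21% of 0.18. That variation is already in the standard error and should not be counted again as bias.

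It can also be said that the sensitivity models carry some route information through length of stay. That depends on how length of stay, ICU days and inpatient rehabilitation days are coded for someone never admitted, which the plan does not say. Coded as zero, they act partly as a route indicator; coded as missing, a complete-case model would drop the whole group.

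**Conclusion.** The mismatch between the widened population and the analysis plan is real and can be read directly from the text. Section F and Aim 1 refer only to hospital discharge, and entry route is in neither the primary model nor the listed sensitivity covariates.

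The statistical cost is modest: roughly 0–3 points of power, assuming shares of 10–50% and route differences of 0.1–0.2 m/s. It would be close to nil if few non-hospitalised people were enrolled or if route is not prognostic. Bias and type I error are not at issue. This is a worthwhile low-cost improvement to the primary model, plus a supportive analysis that Aim 1 needs as it is worded. The endpoint wording alone would be only an editorial correction.

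**What to change.** 1. **Primary regression:** add an indicator of entry route (discharged from hospital, or deconditioned without admission) beside treatment group and baseline gait speed. Cost: 1 df, with little or no gain if route is not prognostic.
2. **Supportive analysis:** pre-specify the same model (without the route term, which is then constant) in hospital-discharged participants, labelled as answering Aim 1 as worded. Cost: a smaller sample and a wider interval, as in step 6 of the working.
3. **Endpoint wording in section F:** align it with D2.1, as day 60 from discharge, or from baseline for those not hospitalised.
4. **Sensitivity models:** state how the hospital-stay covariates are coded for participants who were never admitted.

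None of this needs new visits, participants or data collection. It should be fixed before unblinding.
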